Appendix 6 - Patient Personalized Clinical Benefit APP

BACKGROUND AND SIGNIFICANCE

Standard paper based questionnaires are typically filled out only during office visits and the questions are predefined by the study or clinic. This reduces the number of data points that are collected during a study and relies heavily on a patient's ability to recall specifics from days to weeks prior to the questions being asked. In addition, many of the questions may be irrelevant to that specific patient. Paper based questionnaires also require a patient or healthcare provider to fill out the forms with identifiable information so the data can be correlated to that patient. The healthcare provider is then required to enter the data into an electronic database after completion, which provides for more chance of error.

The Patient Personalized Clinical Benefit (PPCB) App not only simplifies data entry, by alleviating the need to enter a patient's name or other info, but also limits questions to the three main symptoms bothering each individual patient. In addition, data is automatically uploaded to an electronic database, removing the need for a healthcare provider to input data. This can significantly reduce costs associated with collecting and analyzing data, as well as decrease the chance for error. These questions will be asked once a week (patients will have a reminder setup via the app as to increase adherence) for the entire study duration or until the patient elects to stop taking the questionnaire.

INSTRUCTIONS

The patient will be provided the following instructions for downloading the app.

Patient Instructions for Downloading the PPCB Phone App

iPhone Users

1. Go to the App Store on your iPhone or iPad and search for [insert APP name]:
2. Tap the app.
3. Tap GET on the right side of the screen, then tap Install.
4. If asked, enter your password. You can also use Touch ID for app purchases.
5. The app then downloads to your device.
6. Find the app once it has downloaded and tap on the app icon to open the app
7. Enter the assigned UserID that your study team has provided to you.
8. Then tap START QUESTIONNAIRE

[figure not shown]
Android Users

1. Go to the Play Store on your Android device and search for [insert APP name]:
2. Tap the app.
3. Tap INSTALL, read access needs and tap ACCEPT.
4. The app then downloads to your device.
5. Click OPEN, or find the app on your device and tap on the app icon to open the app
6. Enter the assigned UserID that your study team has provided to you.
7. Then tap START QUESTIONNAIRE

QUESTIONNAIRE

The 3-item phone-based app uses a Likert scale for the patient to rate general symptoms. The app will be accessed and completed weekly to assess self-defined symptoms in cancer patients. In the event that a patient does not have the type of mobile device required to access the APP, the patient will be provided the paper version of the questionnaire (printed in color as per screen shots) to complete. Examples of both the PCBB APP- screen shot and the hard copy PPCB Questionnaire are included below.

PPCB App Screen Shot

Personalized Patient Clinical Benefit Questionnaire- Hard Copy

Instructions for Site: Complete the three patient reported symptoms in provided form and print in color for the patient to complete.

Pt Initials _____

Paper Based PPCB Form

Week # _____

Date:

How would you describe your ...over the past week?

How would you describe your ...over the past week?

How would you describe your ...over the past week?

 0 - As bad as it can be
 1
 2
 3
 4
 5
 6
 7
 8
 9
 10 - As good as it can be

 0 - As bad as it can be
 1
 2
 3
 4
 5
 6
 7
 8
 9
 10 - As good as it can be

 0 - As bad as it can be
 1
 2
 3
 4
 5
 6
 7
 8
 9
 10 - As good as it can be

COMPLIANCE

The compliance rate will be estimated as the number of days in which a report was completed, out of the total number of days in which a report was expected. Usability metrics will include the average duration for each daily assessment. These data may be compared to other lab values or treatment information collected while on study. The results of this questionnaire will not affect the patient’s current treatment.

SECURITY

Data security and integrity is maintained through multi-layered encryption of the communication pathways and tokens using leading industry standards. Communication between the mobile device and the backend service utilizes a Restful interface using HTTPS encryption and authentication tokens. Additionally, no communication to the backend can be achieved without the clientID, which is unique to each user. Data collected from the application is stored within a secured database on the backend. No encryption is performed on data at rest currently, however, this can be enabled as needed. Please note, that even though multiple protocols are being employed to secure the communication pathways, no

personal user information is stored in the database. There is no name, email or any other information that is stored in the database that could be used to identify the individual utilizing the application.

ACCESS AND SUPPORT

The link to the app in the Android "Play Store" or Apple "App Store" can be provided via email or directly searched for using the app name. Initial usability support would be provided by the app support staff. An email distribution list will be set up for any support issues. Any technical issues would be emailed to that distribution list with an expected turnaround time of <24 hrs.

When the app is run on either Android or iOS platforms, the only identifiable information that is sent and used to identify the end user is the initial "ID" that is entered to start the app. The user's IP address, phone model, or phone number are not collected by the app.

DATA ANALYSIS

Frequency distributions and descriptive statistics will be computed on all variables. Any continuous variable with a markedly non-normal distribution will be transformed to more closely approximate a normal distribution.

The compliance rate to weekly reporting will be computed as the number of assessments completed divided by the number of expected assessments. Number of questions completed, duration of each reporting session, and time of day of each reporting session will be analyzed using descriptive statistics. Statistical analysis will employ both daily scores for individual items as well as summary measures (e.g., mean scores computed per item per patient over each 8 week period in which at least 4 surveys are completed). Patient weekly and monthly scores for individual items will be graphically displayed longitudinally using stream plots and mean plots. Mean scores with standard deviations will be computed at each time point (weekly as well as monthly). Mean scores for each individual item over time (weekly and monthly) will be modeled using a generalized linear mixed model with a covariate for time (weeks or months since registration) and a random intercept term per patient. Correlations between items will be assessed using Pearson correlations at fixed time points. The threshold for feasibility is estimated at 70%. Finally, coordinator feedback will be collected via interviews and qualitatively analyzed.

REFERENCES

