6.1.4 Patient Personalized Clinical Benefit (PPCB)

The exploratory objective to assess Patient Personalized Clinical Benefit (PPCB) will be evaluated based on the improvement in disease-related symptoms. The specific disease-related symptoms that are most bothersome for the individual patient will be identified at baseline and followed throughout the trial. Patients will use a trial-specific phone-based application to record the status of their three most bothersome disease-related symptoms at baseline, weekly during the treatment period, and at the EOT visit. The patient will be provided instructions and download and complete the app during the baseline C1/Day 1 visit. The patient will enter their responses directly into the APP via their mobile device using an assigned patient ID and therefore no protected health information (PHI) will be recorded. In the event that a patient does not have the type of mobile device required to access the APP, or the patient chooses not to complete the PPCB via the APP, the patient will be provided a paper questionnaire to complete. The site will record the reason the patient is not utilizing the APP in the source documents. Refer to Appendix 6 for more details on the PPCB App.

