8.3.6.3 Patient Personalized Clinical Benefit

The symptoms identified by each patient and the change across time will be evaluated graphically. The most severe ranking across the three items will be compared at baseline and the EOT visits to determine whether each patient's symptoms have improved across time. The relationship between progression at 6 months by RECIST 1.1 versus the change in rankings from baseline to EOT will be assessed using a Wilcoxon Rank Sum test.

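### Appendix 6 pools PPCB items across patients by slot, although each patient fills the slots with their own symptoms and no stated rule fixes the order

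*Protocol*

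**What the plan says.** Protocol section 6.1.4 makes the instrument personal: "The specific disease-related symptoms that are most bothersome for the individual patient will be identified at baseline and followed throughout the trial". Patients then "record the status of their three most bothersome disease-related symptoms" at baseline, weekly and at end of treatment. Appendix 6 agrees, saying that the app "limits questions to the three main symptoms bothering each individual patient".

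The form has three copies of one stem, "How would you describe your ...over the past week", each with a blank for the symptom and a 0 (worst) to 10 (best) rating. Neither the screening step in section 6.1.7.1 nor the site instruction for the paper form gives an order for the three symptoms.

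The Data Analysis part of Appendix 6 then treats the items as variables common to all patients:

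- "Mean scores for each individual item over time (weekly and monthly) will be modeled using a generalized linear mixed model", with a time covariate and a random intercept per patient. There is no term for symptom type.
- "Correlations between items will be assessed using Pearson correlations at fixed time points".
- Individual item scores shown over time, including mean plots.

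Appendix 6 also gives means with standard deviations at each time point, but does not say whether these are per item.

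Section 8.3.6.3 uses a different measure: "The most severe ranking across the three items will be compared at baseline and the EOT visits". The SAP's only exploratory objective is RECIST 1.1 versus iRECIST, so it adds nothing on PPCB.

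**The concern.** A per-item model needs the item to mean the same thing in every patient. Here item 1 may be pain in one patient and fatigue in the next, and whoever enters the symptoms decides which comes first. The random intercept absorbs differences in level between patients. It does not deal with symptoms that follow different courses while sharing a slot.

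An analyst following Appendix 6 would report three slot trends and three between-slot correlations that could have come out differently, from the same patients and the same scores, had the symptoms been typed in another order. A reader would probably take them for symptom trends and symptom associations, which they are not.

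**Working it through.** The plan states no figure for this analysis, so there is none to reproduce. The check has a textual part and a numerical part.

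**Text.** Three things together produce the problem: symptoms are chosen patient by patient (6.1.4, Appendix 6); no order rule is stated (6.1.7.1, Appendix 6 paper form); and Appendix 6 analyses by item across patients, with no term or grouping for symptom.

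**A two-patient example, with assumed changes.** Suppose pain changes by +2 and fatigue by −1 in both patients.

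- Both enter pain first: item-1 mean change = (2 + 2)/2 = +2; item-2 mean change = (−1 − 1)/2 = −1.
- One enters pain first, the other fatigue first: item-1 = (2 − 1)/2 = +0.5; item-2 = (−1 + 2)/2 = +0.5.
- Mean over all items in either case: (2 − 1)/2 = +0.5.

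Only the last figure does not depend on the order.

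**Illustration at the trial's size.** From the protocol: 24 patients, three items, weekly scores on 0 to 10. Assumed: 13 weekly scores; overall level 5; patient SD 1; residual SD 1; symptom-level SD 1, 1.5 or 2; symptom-slope SD 0.05, 0.1 or 0.2 points per week (low, mid, high); average true slope zero. One data set was drawn per scenario, and slot order was reshuffled within patients 5,000 times. With complete balanced data, the time slope of the random-intercept model equals the mean of the per-patient least-squares slopes. Ranges are the central 95% of reshuffles.

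| Quantity | Low | Mid | High |
|---|---|---|---|
| Item-1 baseline mean | 4.54 to 5.42 | 4.29 to 5.46 | 4.67 to 6.21 |
| Item-1 slope per week | −0.049 to 0.010 | −0.047 to 0.027 | −0.041 to 0.079 |
| Item 1–2 correlation, baseline | −0.33 to 0.51 | 0.04 to 0.56 | −0.12 to 0.53 |
| Three-item baseline mean | 5.01 | 4.90 | 5.43 |
| Three-item slope per week | −0.020 | −0.010 | 0.018 |
| Worst-item baseline mean | 3.88 | 3.38 | 3.38 |

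The last three rows were identical in every reshuffle.

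**Cross-check by formula.** If order is random within patients, the slot mean varies with variance (average within-patient variance of the three values, divisor 3)/24. Ignoring rounding and the limits of the scale, that within-patient variance is expected to be (2/3)(symptom variance + residual variance).

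- Baseline half-width = 1.96 × √[(2/3)(σ² + 1)/24], with σ = 1, 1.5, 2: 0.46, 0.59, 0.73. The simulated half-widths are 0.44, 0.58, 0.77.
- Slope half-width = 1.96 × √[(2/3)(τ² + 1/182)/24], where 182 is the sum of squared centred weeks for 13 points and τ = 0.05, 0.1, 0.2: 0.029, 0.041, 0.070. The simulated half-widths are 0.030, 0.037, 0.060.

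Formula and simulation agree. Over 12 weeks, the simulated slope half-widths amount to 12 × 0.030 = 0.36 up to 12 × 0.060 = 0.72 points, from entry order alone.

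**The case against.** The strongest reply is that little depends on these analyses. Section 8.3.6.2 sends the compliance analysis to Appendix 6, while symptom improvement and its link with progression are analysed in 8.3.6.3 with the worst of the three items, which does not depend on slot order. The Appendix 6 model has no treatment term, so no comparison of arms rests on it. All of this stands, and it is why the point is minor.

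Three stronger readings are tempting, and the documents support none of them.

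- *That the PPCB results have no clinical meaning.* Appendix 6 also plans summaries per item per patient, and 8.3.6.3 plots each patient's symptoms over time. These stay within a patient and are sound. All items share one 0–10 scale, so if order is truly arbitrary, a slot mean is a noisier estimate of overall symptom status. The trouble is that it will be read as something more specific.
- *That the association with progression is compromised.* It uses the order-free worst-of-three score.
- *That the worst-of-three score should itself be replaced by a mean.* It does show no change when 4,4,4 becomes 9,9,4, but that is what it is defined to do. A mean has the opposite weakness: 4,4,4 to 9,9,0 rises from 4 to 22/3 − 4/3 = 6 although one symptom is now at its worst. Choosing between them is a preference, not a correction.

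It is also fair that the app screenshot is not in the text available, so an ordering shown on the screen cannot be ruled out. If sites in fact listed symptoms from most to least troublesome, the slots would gain a meaning, but no visible text requires it. Finally, the simulated slopes were centred on zero, which makes a change of sign easy. A common trend well beyond about 0.03 to 0.06 points per week would keep its sign under those assumptions.

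**Conclusion.** The point holds for the pooled per-item mixed models, the between-item correlations, and any mean plots or means pooled by slot. As worded, these mix symptoms and change with an entry order that the protocol does not define. That conclusion follows from the text and needs no simulation.

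The size does rest on assumed values. Under them, reordering alone moves the item-1 baseline mean by about ±0.4 to ±0.8 points, can reverse the item-1 slope in all three scenarios, and can reverse the item 1–2 correlation in the low and high scenarios but not, within the central 95%, in the mid one.

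The compliance rate, the 70% feasibility threshold, the within-patient summaries and the analysis in 8.3.6.3 are untouched. The affected analyses are exploratory and do not compare arms, so the change is worth making but nothing important depends on it.

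**What to change.** In Appendix 6, Data Analysis:

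1. Replace the per-item mixed models, the means and mean plots pooled by item, and the between-item correlations with one score per patient-week: the mean of that patient's three items, 0 worst to 10 best. Fit it in the same mixed model (time, random patient intercept).
2. Code the recorded symptoms to common terms and add descriptive summaries by symptom. This is at most 24 × 3 = 72 entries.
3. Keep the within-patient displays and the compliance analysis as they are.

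Leave the worst-of-three measure in 8.3.6.3 as the prespecified measure. It complements the mean score, which can hide one worsening symptom behind two that improve.

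The cost is a change of wording in one appendix and a small amount of coding. No new data are needed, and neither the primary analysis nor the SAP is affected.

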Primary: To estimate the percentage of patients progressing at 6 months by RECIST1.1 when maintained on a combination regimen of paricalcitol plus pembrolizumab versus pembrolizumab alone.

Secondary:

1. Evaluate the toxicity of the combination of paricalcitol plus pembrolizumab versus pembrolizumab alone.
2. Evaluate the difference in overall survival (OS) in patients administered the combination of paricalcitol plus pembrolizumab versus pembrolizumab alone.
3. Define the impact of the combination of paricalcitol and pembrolizumab on tumor mutational landscape and transcriptional programs.
4. Identify cellular VDR targets in the immune microenvironment with PD1 blockade.

Exploratory:

1. Evaluate the difference in disease progression according to iRECIST vs. RECIST 1.1 criteria (Appendix 5)
2. Assess the utility of a Patient Personalized Clinical Benefit (PPCB) phone-based

| |
|---|
| 
application
 
 3. Assess the association between improvement in symptoms as recorded by the Patient Personalized Clinical Benefit (PPCB) with progression at 6 months by RECIST 1.1 4. Assess any changes in tumor and/or tissue texture on imaging in both arms of the trial 5. To monitor and compare the gut microbial communities in both arms of the trial. |
| 
Trial Design: Randomized Double Blind, Placebo Controlled
 |
| 
No. Patients: Total of 24, 12 randomized to each treatment arm
 |
| 
Name, dose of drugs:
 
 • Pembrolizumab (Keytruda®) 200 mg administered as an intravenous infusion over 30 minutes every 3 weeks. • Paricalcitol (Zemlar®) 25 mcg administered intravenously 3 times per week (given on days 1, 3, 5, 8, 10, 12, 15, 17, 19 ± 1 day of each 21 day cycle) and prior to each pembrolizumab infusion. • Placebo- equivalent volume administered intravenously, 3 times per week and prior to each pembrolizumab infusion. |
| 
Treatment Arms: Arm1: pembrolizumab + paricalcitol Arm 2: pembrolizumab + placebo (saline solution)
 |
| 
Patient Population: Patients with stage IV pancreatic cancer who have been put in best response, defined as: Must have obtained a best response of at least stable disease (SD) or partial response (PR) for a period of 2 months with no further shrinkage of ≥ 30% on scan.
 |

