3.6 Exploratory Endpoints

- Difference in disease progression according to RECIST 1.1 and iRECIST (Appendix 5) criteria
- Compliance rate responding to a phone - based application for the assessment of patient defined symptoms
- Improvement in symptoms as recorded by the Patient Personalized Clinical Benefit (PPCB)
- Differences in tumor and/or tissue texture on CT scan between the two treatment arms
- Differences in gut microbial communities within and between fecal samples using alpha and beta diversity metrics based on 16S rRNA sequencing

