4.8 Patient Withdrawal/Discontinuation Criteria

Patients may withdraw consent at any time for any reason or be dropped from the trial at the discretion of the investigator should any untoward effect occur. In addition, a patient may be withdrawn by the investigator or the Sponsor if enrollment into the trial is inappropriate, the trial plan is violated, or for administrative and/or other safety reasons. Specific details regarding assessments to be done at an End of Treatment (EOT) visit at time of discontinuation or withdrawal are provided in Section 6.1.7.3.

A patient must be discontinued from the trial for any of the following reasons:

- The patient or legal representative (such as a parent or legal guardian) withdraws consent.
- Confirmed disease progression
- Unacceptable adverse experiences as described in Section 4.2.4
- Inter-current illness that prevents further administration of treatment
- Investigator's decision to withdraw the patient
- The patient has a confirmed positive serum pregnancy test
- Noncompliance with trial treatment or procedure requirements
- The patient is lost to follow-up
- Completed 24 months of uninterrupted treatment with pembrolizumab or 35 cycles of trial treatment whichever is later. 24 months of trial medication is calculated from the date of first dose.
- Administrative reasons

The End of Treatment and Follow-up visit procedures are listed in Section 5 (Trial Schedule) and Section 6.1.7 (Visit Requirements). After the end of treatment, each patient will be followed for 30 days for adverse event monitoring (serious adverse events will be collected for 90 days after the end of treatment as described in Section 6.2.3.1). Patients who discontinue for reasons other than progressive disease will have post-treatment follow-up every 90 days for disease status until disease progression, initiating a non-study cancer treatment, withdrawing consent or becoming lost to follow-up, or the end of the trial, whichever occurs first.

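### The PPCB symptom-trend model has a random intercept only, so its interval for change over time is too narrow if patients differ in trend or weekly scores are correlated

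*Protocol*

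**What the plan says.** The Data Analysis part of Protocol Appendix 6 states that "Mean scores for each individual item over time (weekly and monthly) will be modeled". The form of the model is given later in the same sentence: "generalized linear mixed model with a covariate for time (weeks or months since registration) and a random intercept term per patient". The appendix names no random slope, residual correlation structure, robust standard error, small-sample correction or treatment term. It also names no distribution or link, and no test, alpha or sidedness for the time coefficient.

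The data behind the model are as follows.

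- Section 6.1.4: patients "record the status of their three most bothersome disease-related symptoms at baseline, weekly during the treatment period, and at the EOT visit". The symptoms are chosen by each patient.
- Appendix 6: "These questions will be asked once a week", each item on a 0 to 10 scale whose top is labelled "10 - As good as it can be".
- Synopsis: "Total of 24, 12 randomized to each treatment arm".
- Section 4.8: a treatment limit of "Completed 24 months of uninterrupted treatment with pembrolizumab or 35 cycles of trial treatment whichever is later". At three weeks per cycle, 35 cycles are 105 weeks.

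Section 8.3.6.2 refers to Appendix 6 for compliance with the app. Section 8.3.6.3 analyses symptom change separately: graphs, a per-patient comparison of the worst item at baseline and EOT, and a Wilcoxon test of that change against 6-month progression. The SAP does not cover PPCB.

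**The concern.** With a random intercept only, any difference between patients in trend falls into a residual that the model treats as independent from week to week. The standard error of the time effect then falls with the number of weekly reports, when the evidence on an average trend is limited by the number of patients, at most 24. Serial correlation within a patient has the same effect.

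Three features of the trial make equal slopes and independent residuals unlikely:

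- patients rate different self-chosen symptoms in the same item slot;
- both arms are pooled with no treatment term;
- the length of weekly follow-up varies widely, so the longest-treated patients dominate the slope.

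This is the only regression model of the score course in the plan. If its time effect is reported with an interval, chance drift in a few long-treated patients could look like a firm average improvement or worsening.

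**Working it through.** The plan states no error rate or power for this model, so there is no figure to reproduce.

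**Inputs from the documents.** N = 24; weekly scores from 0 to 10; treatment for up to about 105 weeks. The planned 6-month progression-free rates (8% and 58%, section 8.2) are used only to generate length of follow-up.

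**Assumptions, not in the documents.** Two-sided 5% level; normal scores with identity link; residual SD σ = 1.5 (range 1.0 to 2.0); intercept SD 2; between-patient slope SD τ from 0 to 0.10 points per week. For scale, τ = 0.05 is 0.05 × 26 = 1.3 points over 26 weeks. The true mean slope is zero.

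**Closed form, T weekly scores for every patient.** Sxx = T(T² − 1)/12.

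- True variance of the estimated slope: (τ² + σ²/Sxx)/N.
- Variance reported by the random-intercept model, approximately: [σ² + τ²·Sxx·(N − 1)/(N(T − 1) − 1)]/(N·Sxx).
- False-positive rate: 2[1 − Φ(1.96/√R)], where R is true over reported variance.

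For T = 27 and τ = 0.05:

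- Sxx = 27 × 728/12 = 1638.
- True variance = (0.0025 + 2.25/1638)/24 = 0.0001614.
- Reported variance = [2.25 + 0.0025 × 1638 × 23/623]/(24 × 1638) = 2.401/39312 = 0.0000611.
- R = 2.64 and √R = 1.63, so the stated standard error is too small by a factor of about 1.6.
- The rate is 2[1 − Φ(1.21)] = 23%.

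For T = 10 and τ = 0.10:

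- Sxx = 82.5.
- True variance = (0.01 + 2.25/82.5)/24 = 0.001553.
- Reported variance = [2.25 + 0.825 × 23/215]/1980 = 0.001181.
- R = 1.32, and the rate is 9%.

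**Simulation.** Random-intercept fits and Wald tests, with follow-up drawn from the 8% and 58% rates and capped as shown.

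| Slope SD per week | Closed form, 10 scores | Closed form, 27 scores | Simulated, 26-27 weeks, σ = 1.5 | Simulated, to 105 weeks, σ = 1.0-2.0 |
|---|---|---|---|---|
| 0 | 5% | 5% | 4-5% | about 6% |
| 0.025 | 5% | 10% | about 11% | 54-72% |
| 0.05 | 6% | 23% | 19-23% | 70-80% |
| 0.10 | 9% | 44% | 38-46% | 73-83% |

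Further results:

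- With σ varied from 1.0 to 2.0 and a 27-week cap, the rates are 7-14% at τ = 0.025, 16-34% at 0.05 and 33-54% at 0.10.
- If both arms progress at the control rate and reporting runs to 105 weeks, the rates are 13-32% at 0.025 and 28-53% at 0.05.
- Monthly means do not cure it: 18% at 0.05 and 34% at 0.10 (σ = 1.5, 27-week cap).
- Equal slopes with weekly residual autocorrelation of 0.4 give 16-19%; autocorrelation of 0.5 gives 24%.

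**Why long follow-up matters.** Under the stated model a patient's weight on the slope is proportional to Sxx. For 105 reports Sxx = 105 × 11024/12 = 96,460. One such patient carries the weight of 96,460/1638 ≈ 59 patients with 27 reports each.

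**After the fix** (300 runs per cell, Monte Carlo SE about 1.3 points, σ = 1.5). The setting lines refer to a 27-week cap and the planned progression rates:

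- τ = 0.10: 45% falls to 7% with a random slope and normal reference, and to 6% with t on 23 df.
- τ = 0.05: 27% in this batch falls to 10% and 9%.
- A t test on per-patient slopes gives 3-7% across the slope-SD settings checked, and 4-6% in a check that included autocorrelation of 0.4.

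**The case against.** The strongest reply is that the plan declares nothing from this model. Appendix 6 attaches no hypothesis, level or decision rule to the time coefficient, and the surrounding text is descriptive: plots, means with SDs, correlations. The two-tailed 0.05 rule in the next appendix belongs to the texture analysis. This stands. The error rates above rest on a level supplied here and serve as a measure of how far the interval is too narrow. A mixed-model slope is normally reported with its standard error, and that quantity is wrong whether or not a p-value is printed.

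Three stronger readings are tempting and are not supported.

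- *The endpoint "Improvement in symptoms as recorded by the Patient Personalized Clinical Benefit (PPCB") is compromised.* It is not. Section 8.3.6.3 analyses it with one change per patient, which does not have this problem.
- *The planned 8% and 58% show that symptom courses differ.* Section 8.2 concerns radiographic progression and says nothing on symptom scores. Unequal slopes are plausible for the reasons given under the concern, but no figure in the documents demonstrates them.
- *The model will report a false trend far too often.* The size depends on a slope SD, residual SD and reporting length that the documents do not give. With about 10 reports per patient the rate is close to nominal.

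It is also fair to say that the analysis is exploratory, has no treatment term, and could be labelled descriptive. That sets the priority low. It does not make the interval right.

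**Conclusion.** The point holds in a conditional form. The standard error and interval for the PPCB time effect ignore between-patient differences in trend and week-to-week correlation, and nothing elsewhere in the protocol or SAP repairs this. Either feature makes the interval too narrow, and both are likely here.

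On the assumptions listed, over about 27 weeks with residual SD 1.5, a nominal 5% becomes 10-11%, about 20% and about 40-45% at slope SDs of 0.025, 0.05 and 0.10 points per week. It becomes 16-19% from autocorrelation of 0.4 alone. The problem is small with short follow-up and large if reporting continues towards 24 months.

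A reader might infer that a treatment comparison or the trial's main conclusions are at risk. They are not: the model pools the arms, and no primary or secondary analysis uses it. This is a minor-priority, cheap improvement.

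**What to change.** In Appendix 6, Data Analysis, replace the random-effects clause at the end of the model sentence with:

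> a random intercept and a random slope for time per patient, with small-sample (Kenward-Roger or Satterthwaite) degrees of freedom; if this does not converge, estimate one slope per patient and test the mean slope across patients with a t test.

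The fallback should be written in advance, because random-slope fits often gave convergence warnings in simulated data of this size, and one setting still showed 9-10% after the change. The cost is one sentence and no new data. The downside is a wider interval and occasional use of the fallback, which weights patients equally and needs at least two reports from each. If the team intends no inference from this model, saying so in Appendix 6 and reporting the slope without a p-value or interval would also settle the point.
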